### **3. PATIENT SELECTION**

#### **3.1 Eligibility Criteria**

- 3.1.1 Patients must have histologically proven stage IIIB, IV or recurrent non-small cell lung cancer. Patients must be willing to undergo a pre-treatment tumor biopsy, either core needle biopsy or equivalent amount or via excisional specimen (cytology specimen not acceptable for this purpose).
- 3.1.2 Patients must have measurable disease, defined as at least one lesion that can be accurately measured in at least one dimension (longest diameter to be recorded for non-nodal lesions and short axis for nodal lesions) as  $\geq 20$  mm with conventional techniques or as  $\geq 10$  mm with spiral CT scan, MRI, or calipers by clinical exam. See Section 11 for the evaluation of measurable disease. A CT scan of the abdomen and pelvis is not required for patients with no disease in these areas.
- 3.1.3 Age  $\geq 18$  years.  
Because no dosing or adverse event data are currently available on the use of azacitidine with entinostat, or of Nivolumab, in patients  $<18$  years of age, children are excluded from this study.
- 3.1.4 Eastern Cooperative Oncology Group (ECOG) performance status 0 to 1.
- 3.1.5 Life expectancy of greater than 12 weeks.
- 3.1.6 Patients must have normal organ and marrow function as defined below:

|                             |   |
|-----------------------------|---|
| - leukocytes                | $\geq 2,000/\text{mcL}$                             |
| - absolute neutrophil count | $\geq 1,500/\text{mcL}$                             |
| - platelets                 | $\geq 100,000/\text{mcL}$                           |
| - total bilirubin           | within normal institutional limits                  |
| - AST(SGOT)/ALT(SGPT)       | $\leq 3 \times$ institutional upper limit of normal |
| - creatinine                | within normal institutional limits                  |

OR

|   |  |
|---|--|
| - creatinine clearance                          | $\geq 40 \text{ mL/min}$ for patients with creatinine levels above institutional normal. |
| - Resting and walking O 2 saturation | must remain above 90% at the time of screening   |

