## 8. STUDY CALENDARS

Pre-study laboratory and exam evaluations are to be conducted within 2 weeks prior to start of protocol therapy. Pre-study scans and x-rays must be done  $\leq 4$  weeks  $\pm 1$  week prior to the start of therapy. In the event that the patient's condition is deteriorating, laboratory evaluations should be repeated within 48 hours prior to initiation of the next cycle of therapy. ***All time points on study have leeway of plus or minus 3 days unless otherwise noted.***

**NOTE:** *In order to minimize the need for research-only in-person visits, telemedicine visits may be substituted for in-person clinical trial visits or portions of clinical trial visits where determined to be appropriate and where determined by the investigator not to increase the participants risks. Prior to initiating telemedicine for study visits the study team will explain to the participant, what a telemedicine visit entails and confirm that the study participant is in agreement and able to proceed with this method. Telemedicine acknowledgement will be obtained in accordance with the Guidance for Use of Telemedicine in Research. In the event telemedicine is not deemed feasible, the study visit will proceed as an in-person visit. Telemedicine visits will be conducted using HIPAA compliant method approved by the Health System and within licensing restrictions.*

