#### 9.1.1 Definitions

Evaluable for toxicity. All patients will be evaluable for toxicity from the time of their first treatment on protocol.

Evaluable for objective response. Response to azacitidine/entinostat and to Nivolumab, will be assessed separately. For each, only those patients who have measurable disease present at baseline, have received at least one cycle of therapy, and have had their disease re-evaluated will be considered evaluable for response. These patients will have their response classified according to the definitions stated below. (Note: Patients who exhibit objective disease progression prior to the end of the first cycle of either therapy will also be considered evaluable.)

Evaluable Non-Target Disease Response. Patients who have lesions present at baseline that are evaluable but do not meet the definitions of measurable disease, have received at least one cycle of therapy, and have had their disease re-evaluated will be considered evaluable for non-target disease. The response assessment is based on the presence, absence, or unequivocal progression of the lesions.

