#### 9.1.2 Disease Parameters

To assess objective response or future progression, it is necessary to estimate the overall tumor burden at baseline and use this as a comparator for subsequent measurements. Measurable disease is defined by the presence of at least one measurable lesion.

Measurable disease. Measurable lesions are defined as those that can be accurately measured in at least one dimension (longest diameter to be recorded) as  $\geq 20$  mm by chest x-ray or as  $\geq 10$  mm with CT scan, MRI, or calipers by clinical exam. All tumor measurements must be recorded in millimeters (or decimal fractions of centimeters).

Note: Tumor lesions that are situated in a previously irradiated area are not considered measurable unless there has been demonstrated progression in the lesion.

Malignant lymph nodes. To be considered pathologically enlarged and measurable, a lymph node must be  $\geq 15$  mm in short axis when assessed by CT scan (CT scan slice thickness recommended to be no greater than 5 mm). At baseline and in follow-up, only the short axis will be measured and followed.

Non-measurable disease. All other lesions (or sites of disease), including small lesions (longest diameter  $<10$  mm or pathological lymph nodes with  $\geq 10$  to  $<15$  mm short axis), are considered non-measurable disease. Bone lesions, leptomeningeal disease, ascites, pleural/pericardial effusions, lymphangitic involvement of the skin or lung, inflammatory breast disease, and abdominal masses/abdominal organomegaly (not followed by CT or MRI), are considered as non-measurable.

Note: Cystic lesions that meet the criteria for radiographically defined simple cysts should not be considered as malignant lesions (neither measurable nor non-measurable) since they are, by definition, simple cysts.

'Cystic lesions' thought to represent cystic metastases can be considered as measurable lesions, if they meet the definition of measurability described above. However, if non-cystic lesions are present in the same patient, these are preferred for selection as target lesions.

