#### 9.1.3 Methods for Evaluation of Measurable Disease

All measurements should be taken and recorded in metric notation using a ruler or calipers. All baseline evaluations should be performed as closely as possible to the beginning of treatment and never more than 4 weeks before the beginning of the treatment.

The same method of assessment and the same technique should be used to characterize each identified and reported lesion at baseline and during follow-up. Imaging-based evaluation is preferred to evaluation by clinical examination unless the lesion(s) being followed cannot be imaged but are assessable by clinical exam.

**Clinical lesions** Clinical lesions will only be considered measurable when they are superficial (e.g., skin nodules and palpable lymph nodes) and  $\geq 10$  mm diameter as assessed using calipers (e.g., skin nodules). In the case of skin lesions, documentation by color photography, including a ruler to estimate the size of the lesion, is recommended.

**Chest x-ray** Lesions on chest x-ray are acceptable as measurable lesions when they are clearly defined and surrounded by aerated lung. However, CT is preferable.

**Conventional CT and MRI** This guideline has defined measurability of lesions on CT

scan based on the assumption that CT slice thickness is 5 mm or less. If CT scans have slice thickness greater than 5 mm, the minimum size for a measurable lesion should be twice the slice thickness. MRI is also acceptable in certain situations (e.g. for body scans).

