#### 9.1.4 Response Criteria

##### 9.1.4.1 Evaluation of Target Lesions

Complete Response (CR): Disappearance of all target lesions. Any pathological lymph nodes (whether target or non-target) must have reduction in short axis to <10 mm.

Partial Response (PR): At least a 30% decrease in the sum of the diameters of target lesions, taking as reference the baseline sum diameters.

Progressive Disease (PD): At least a 20% increase in the sum of the diameters of target lesions, taking as reference the smallest sum on study (this includes the baseline sum if that is the smallest on study). In addition to the relative increase of 20%, the sum must also demonstrate an absolute increase of at least 5 mm. (Note: the appearance of one or more new lesions is also considered progressions).

Stable Disease (SD): Neither sufficient shrinkage to qualify for PR nor sufficient increase to qualify for PD, taking as reference the smallest sum diameters while on study.

Special notes on the assessment of target lesions:

**Lymph nodes:** Lymph nodes identified as target lesions should always have the actual short axis measurement recorded and should be measured in the same anatomical plane as the baseline examination, even if the nodes regress to below 10mm on study. This means that when lymph nodes are included as target lesions, the 'sum' of lesions may not be zero even if complete response criteria are met, since a normal lymph node is defined as having a short axis of < 10 mm.

**Target lesions that become 'too small to measure':** All lesions (nodal and non-nodal) recorded at baseline should have their actual measurements recorded at each subsequent evaluation, even when very small (eg, 2mm). If the radiologist is able to provide an actual measure, that should be recorded, even if it is below 5mm. When such a lesion becomes difficult to assign an exact measurement, it is recommended to: If it is in the opinion of the radiologist that the lesion has likely disappeared, the measurement should be recorded as 0 mm. If the lesion is believed to be present and is faintly seen but too small to measure, a default value of 5 mm should be assigned (note: in case of a lymph node believed to be present and faintly seen but too small to measure, a default value of 5 mm should be assigned in this circumstance as well). This default value is derived from the 5 mm CT slice thickness (but should not be changed with varying CT slice thickness).

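### Eligibility accepts lymph nodes of 10 to <15 mm as measurable disease but Section 9 does not, so an eligible patient can be unevaluable for response; the baseline-scan windows also conflict

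*Combined protocol and SAP*

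**What the plan says.** **Measurable disease at entry.** Section 3.1.2 requires at least one measurable lesion. It names the dimension for each lesion type ("longest diameter to be recorded for non-nodal lesions and short axis for nodal lesions") and then gives one limit for both types: ≥20 mm with conventional techniques, or ≥10 "mm with spiral CT scan, MRI, or calipers by clinical exam". For detail it directs the reader elsewhere: "See Section 11 for the evaluation of measurable disease". Section 11 is the biomarker section; measurable disease is dealt with in Section 9.

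**Measurable disease for response.** Section 9.1.2 has a separate nodal rule: "To be considered pathologically enlarged and measurable, a lymph node must be" ≥15 mm in short axis on CT. It lists nodes of 10 to <15 mm as non-measurable. Section 4.4.1 also uses 15 mm for new nodal lesions.

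**Who counts for the primary endpoint.** Section 10.1.2 measures response as Section 9 describes. Section 9.1.1 counts as evaluable for objective response "only those patients who have measurable disease present at baseline" and who also had at least one cycle and a re-evaluation. For complete response, Section 9.1.4.1 says that pathological nodes "must have reduction in short axis to <10 mm"; partial response needs a 30% fall in the sum of diameters.

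**Age of the baseline scan.** Section 8: "Pre-study scans and x-rays must be done" no more than 4 weeks, ±1 week, before therapy starts. Section 9.1: within 4 weeks before therapy. Section 9.1.3: "never more than 4 weeks before the beginning of the treatment". Section 1.1: within 4 weeks of enrollment.

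**The concern.** Entry and evaluation use different definitions of the same term, and no other section reconciles them. Section 3.2 rules out eligibility waivers, so sites can be expected to apply 3.1.2 as worded, and its pointer does not lead them to the 15 mm rule. A patient can therefore meet every entry criterion, have the required biopsies, receive all three drugs, and still contribute nothing to the response rate. With 20 patients planned per arm, a few such losses matter.

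The scan windows are a second, lesser conflict at the same baseline: a site that follows the calendar can breach Section 9.1.3.

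**Working it through.** **1. Same node, two sections (CT, short axis).**

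| Short axis | Section 3.1.2 | Section 9.1.2 |
|---|---|---|
| <10 mm | not measurable | not measurable |
| 10 to <15 mm | measurable | non-measurable |
| ≥15 mm | measurable | measurable |

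The conflict is confined to the middle row.

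**2. One patient followed through.** Take a patient with a 12 mm node and otherwise only bone lesions or an effusion, which 9.1.2 lists as non-measurable. Section 3.1.2 is met. The baseline and Cycle 2 biopsies in Section 8 are required and treatment is given. Under 9.1.1 there is no measurable disease at baseline, so the patient is not evaluable for objective response. Section 9.1.1 does have a category for non-target disease, but it is separate from objective response. Its note on progression before the end of the first cycle could at most bring back early progressors, that is, non-responders.

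**3. Room for unevaluable patients (Section 10.2).** The stated 22 per arm reproduces as 20 × 1.10 = 22, leaving 22 − 20 = 2 places. For a total unevaluable rate u from all causes,

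P(more than 2 of 22) = 1 − Σ(k = 0 to 2) C(22,k) u^k (1−u)^(22−k).

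| u (5% and 15% assumed; 10% is the plan's allowance) | P(more than 2) |
|---|---|
| 5% | 9.5% |
| 10% | 38% |
| 15% | 66% |

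If the true rate equals the 10% allowed for, the two places are already exceeded 38% of the time. Any small-node patients add to that rate.

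**4. Effect on the Arm E/F futility look (Section 10.4).** The rule stops an arm at 0 responses in 15, so Pr(stop) = (1−p)^15. At p = 0.10, 0.9^15 = 0.206, which matches the plan's table. Section 10.4 counts patients and does not say how unevaluable ones are treated. If two of the 15 were unevaluable and counted as non-responders (assumed), Pr(stop) = 0.9^13 = 0.254.

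**5. If a site used the node as its sole target, contrary to Section 9.** Shrinkage to reach 9 mm, in whole millimetres:

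| Baseline | Change to 9 mm | Percent |
|---|---|---|
| 10 mm | 1 mm | 10% |
| 11 mm | 2 mm | 18% |
| 12 mm | 3 mm | 25% |
| 13 mm | 4 mm | 31% |
| 14 mm | 5 mm | 36% |
| 15 mm | 6 mm | 40% |

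For 10–12 mm nodes the complete-response cut needs less shrinkage than the 30% for partial response. At 13 mm and above it does not.

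**6. Scan age.** Section 8 allows 4 + 1 = 5 weeks; Section 9 allows 4. Section 1.1 counts from enrollment, so scan age at first dose also depends on the gap between enrollment and treatment. For one extra week, diameter grows by a factor 2^(7/(3×T)), where T is the volume doubling time in days. With T = 75 and 40 (assumed), the factors are 1.022 and 1.041, about 2–4%. Growth before the first dose makes a 30% decrease from the older baseline harder to reach, so it acts against response.

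**The case against.** The strongest reply is that Section 9 already controls the endpoint. Section 10.1.2 refers response to Section 9, and 9.1.2 draws target lesions from measurable lesions, so a 10 to <15 mm node should never become a target. Best response also has to be confirmed: 9.1 asks for a repeat scan at least 4 weeks later, and 9.1.4.3 requires more than 4 weeks for a target-lesion complete response. A single 9 mm reading is not a response. The required biopsies also make patients with only small nodes less likely. All of this stands, and it reduces the easy-response scenario to a secondary risk. It does not help the patient who is admitted under 3.1.2 and then excluded under 9.1.1, because that exclusion is what following Section 9 produces.

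A reader might go further and infer that false nodal responses could carry Arm E or F through. With a true response rate of 0% and a false-response rate of 1%, 2% or 5% per patient, 1 − (1−e)^15 gives a 14%, 26% or 54% chance of getting past the 15-patient look. The arithmetic is right, but the documents give no share of node-only patients and no misclassification rate, and these would have to be confirmed false responses across all patients. Nor does one response make an arm succeed: it only avoids the rule that zero responders is not promising. Section 10.4 calls a rate of at least 10% encouraging, 1/20 is 5%, and the final analysis is descriptive.

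A reader might also infer that an older scan makes a patient unevaluable. Section 9.1.1 does not list scan age as a ground.

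**Conclusion.** The nodal conflict is real in the current text and should be corrected. Its main consequence is an eligible, biopsied and treated patient who cannot be evaluated for the primary endpoint, in arms with room for two such losses from all causes. How many patients this would involve cannot be told from the documents; the probabilities in steps 3 and 4 illustrate sensitivity and are not forecasts. The response-inflation route exists only if a site departs from Section 9, only for sole-target nodes of 10–12 mm, and only if the change is confirmed; the 1 mm case is the extreme.

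The scan-window conflict is a compliance contradiction. Its effect is small under the assumed doubling times, runs against response, and does not alter evaluability. The plan's stated operating characteristics are not in question.

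**What to change.** - Section 3.1.2: add a limit of ≥15 mm short axis for lymph nodes, to match 9.1.2, and change the pointer from Section 11 to Section 9.
- Baseline scan: use one window in 1.1, 8, 9.1 and 9.1.3, namely no more than 4 weeks before first dose, as Section 9 already states. In practice this removes the ±1 week for baseline scans in Section 8 and re-anchors Section 1.1 from enrollment to first dose.

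The cost is a few wording edits, a few patients with only small nodes who become ineligible, and an occasional repeat scan.

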### 3.1.11 Arm-specific eligibility criteria

3.1.11.1 Arm D: Anti-PD-1/PD-L1 treatment naïve patients only

3.1.11.2 Arm E & F: Anti-PD-1/PD-L1 treatment experienced patients: Patients must have had refractory (Arm E=less than 24 weeks from first dose of anti-PD-

1/PD-L1) or recurrent (Arm F=more than 24 weeks from first dose of anti-PD-1/PD-L1) disease during or after anti-PD-1 or anti-PD-L1 therapy and, in the opinion of the investigator, must be unlikely to benefit from nivolumab monotherapy.

3.1.13 Patients must have disease amenable to biopsy at the time of enrollment as biopsies are required for study participation (see Study Calendar **Section 8**, for biopsy schedule by Arm).

### 3.2 **Exclusion Criteria**

3.2.1 Any active history of a known autoimmune disease. Subjects with vitiligo, type 1 diabetes mellitus, residual hypothyroidism requiring hormone replacement, or conditions not expected to recur in the absence of an external trigger are permitted to enroll.

3.2.2 Subjects with a history of interstitial lung disease or lung disease that has required intubation in the past (i.e. such as Asthma or COPD)..

3.2.3 Patients who have had chemotherapy within 2 weeks (6 weeks for nitrosoureas or mitomycin C) prior to entering the study or those who have not recovered from adverse events due to agents administered more than 2 weeks earlier.

3.2.4 Patients who have had radiation therapy within 1 week prior to entering the study.

3.2.5 Patients who are receiving any other anticancer therapy.

3.2.6 Patients with uncontrolled brain metastases. Patients with brain metastases must have stable neurologic status following local therapy (surgery or radiation) for at least 2 weeks without the use of steroids or on stable or decreasing dose of  $\leq 10\text{mg}$  daily prednisone (or equivalent), and must be without neurologic dysfunction that would confound the evaluation of neurologic and other adverse events. Patients with a history of carcinomatous meningitis are not eligible.

3.2.7 History of allergic reactions attributed to compounds of similar chemical or biologic composition to entinostat, azacitidine, or Nivolumab.

3.2.8 Known or suspected hypersensitivity to azacitidine or mannitol

3.2.9 Uncontrolled inter-current illness including, but not limited to, ongoing or active infection, symptomatic congestive heart failure, unstable angina pectoris, uncontrolled cardiac arrhythmia, myocardial infarction or new onset angina within six months of enrollment, or psychiatric illness/social situations that would limit compliance with study requirements.

3.2.10 Pregnant women are excluded from this study because entinostat, azacitidine, and Nivolumab are agents with the potential for teratogenic or abortifacient effects. Because there is an unknown but potential risk for adverse events in nursing infants

secondary to treatment of the mother with entinostat, azacitidine, or Nivolumab breastfeeding should be discontinued if the mother is treated on this protocol.

- 3.2.11 HIV-positive patients are excluded. (Patients cannot have known history of HIV. Testing for it at baseline is not required unless it is suspected they may have it).
- 3.2.12 Patients with active hepatitis B or hepatitis C are excluded. (Patients cannot have known history of hepatitis B or hepatitis C. Testing for it at baseline is not required unless it is suspected they may have it).
- 3.2.13 Patients with a condition requiring systemic treatment with either corticosteroids (>10 mg daily prednisone equivalent) or other immunosuppressive medications within 14 days of randomization. Inhaled or topical steroids and adrenal replacement steroid doses  $\leq$  10 mg daily prednisone equivalent, are permitted in the absence of active autoimmune disease.
- 3.2.14 Patients with malabsorption in the small intestine or other conditions that would preclude administration of oral medication.
- 3.2.15 Prior therapy with DNA methyltransferase therapy or HDAC inhibitor therapy.

Patients must meet all inclusion criteria and none of the exclusion criteria. Eligibility Waivers will not be granted.

### **3.3 Inclusion of Women and Minorities**

Both men and women of all races and ethnic groups are eligible for this trial.

## **4. TREATMENT PLAN**

### **4.1 Agent Administration**

Patients will be treated by Arm according to disease status. Treatment will be administered on an outpatient basis. Reported adverse events and potential risks are described in Section 7. Appropriate dose modifications are described in Section 6. No investigational or commercial agents or therapies other than those described below may be administered with the intent to treat the patient's malignancy.

| Regimen description  |  |                      |       |                |              |             |
|-----------------------------|--|----------------------|-------|----------------|--------------|-------------|
| Agents                      | Premedications/instructions                                    | Dose                 | Route | calendar       | Cycle length | # of Cycles |
| Epigenetic component |  |                      |       |                |              |             |
| Arm D-F
Azacitidine      | 5HT3 inhibitor PO or IV 30 min prior; rotate site of injection | 40 mg/m  | SC    | Days 1-5, 8-10 | 28 days      | 6           |
| Arm D-F
Entinostat       | 5HT3 inhibitor PO or IV 30 min prior; on an empty stomach      | 5 mg                 | PO    | Days 3 and 10  |              | Cycles      |

| Immunotherapy component |   |  |    |                        |                    |           |
|-------------------------|---|--|----|------------------------|--------------------|-----------|
| Arm C-F
Nivolumab    | Optional: acetaminophen 650 mg PO and diphenhydramine 50 mg PO/IV 30 min prior. | 240 mg
480 mg
(after
Cycle 6) | IV | Days 1,
15
Day 1 | 28 days
28 days | Until PD^ |

^Patients are allowed to remain on nivolumab monotherapy treatment after the first documented PD if clinically stable. (See Section 4.4.1)

^After a patient has completed 6 months of nivolumab (regardless of arm assignment), they can receive nivolumab every 4 weeks instead of every 2 weeks.

